	Dose escalation visits & 2 nd infusion at highest tolerated dose				Quarterly visits (day 1/wk0, wk12, wk26, wk38, wk52)				Week 64
	Pre-infusion	End of infusion	24 hr	48 hr	Pre-infusion	End of infusion	24 hr	48 hr	
Electrocardiogram	X a	X a	X a	X a	X b	X	X c	X	
Liver function testing	X		X c	X	X		X c	X	X
Clinical chemistry & coagulation					X		X c	X	X
Urinalysis					X				X
Hematology					X d		X c	X	
Safety biomarkers:									
Ceramide	X		X c	X	X		X c	X	X
Cardiac troponin-1	X		X c	X	X		X c	X	X
hsCRP	X		X c	X	X		X c	X	X
Calcitonin	X		X c	X	X		X c	X	X
Iron and ferritin	X		X c	X	X		X c	X	X
IL6 and IL8 e	X		X c	X	X f		X c,f	X f	
Plasma and/or DBS sphingomyelin and metabolite concentrations g	X		X c	X	X		X c	X	X

Note: When multiple assessments are required, the order should be vital signs before ECG before PK or blood draws. Preinfusion assessments are to be completed within 24 hours prior to olipudase alfa infusion. End of infusion assessments are to be completed with 10 minutes following the end of olipudase alfa infusion. Twenty four (24) hour and 48 hour post infusion assessments to be completed within  $\pm$  3 hours of scheduled time.

a At each new dose of  $\geq 0.3$  mg/kg only.

b ECG in triplicate on day 1/week 0

c Sample/assessment is not required in patients in the child cohort (patients aged 6 to <12 years) or in patients aged 3 to < 6 years.

d Two samples to be collected within 24 hours of olipudase alfa at week 52. See [Section 10.3.5](#) for details.

e Sample not required in patients aged 3 to < 6 years.

f Sample not required at week 26, week 38 or week 52.

g DBS collection not required in patients aged 3 to < 6 years.

Abbreviations: hr = hour; hsCRP = high sensitivity C reactive protein; IL = interleukin; wk = week.

**1.4 SUPPLEMENTAL FLOWCHART - DAY 1/WEEK 0, DOSE ESCALATION VISITS, SECOND INFUSION AT THE HIGHEST TOLERATED DOSE, QUARTERLY VISIT AND WEEK 64 ASSESSMENTS IN PATIENTS ≤ 2 YEARS OLD**

	Day 1/Week 0			Dose escalation visits & 2 nd infusion at highest tolerated dose			Quarterly visits (wk12, wk26, wk38, wk52)			Week 64

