In the completed Phase 1 study (5), the safety, pharmacokinetic, and pharmacodynamic profiles of single, ascending doses of olipudase alfa were evaluated (5). Single doses of 0.03, 0.1, 0.3, 0.6, and 1.0 mg/kg olipudase alfa were infused sequentially by dose cohort in 11 adult patients with ASMD. Study results found dose-related increases in ceramide, bilirubin, high sensitivity C-reactive protein (hsCRP), and other acute phase reactants in patients that peaked 24 to 48 hours post-dose and resolved by Day 14. Reported adverse events (AEs) involving constitutional symptoms (pain, fever, nausea, and vomiting) were consistent with first dose-related toxicity and occurred in a dose dependent fashion, as was previously observed in the ASMKO mouse. Serious AEs (SAEs) related to olipudase alfa treatment were not reported. The sponsor terminated the study subsequent to the single patient dosed at 1.0 mg/kg olipudase alfa presenting with hyperbilirubinemia and an acute-phase reaction with clinical symptoms. Of note, this patient was subsequently confirmed to have Gilbert’s syndrome. Because there were no other signs of liver toxicity or hemolysis, the observed hyperbilirubinemia may have been secondary to specific inhibition of bilirubin uptake into hepatocytes and/or glucuronide conjugation of bilirubin within hepatocytes.

In a Phase 1b, open-label, multi-center, ascending dose study (DFI13412) in 5 adult patients with ASMD, the safety and tolerability of olipudase alfa was evaluated during a 26-week treatment period (6). Patients received an initial intravenous dose of 0.1 mg/kg olipudase alfa and then dose-escalated in a step wise manner to a final target intravenous dose of 3.0 mg/kg. All patients remained 3.0 mg/kg for the remainder of the treatment period. Upon completion of the study, all patients enrolled into an open-label, long term treatment study (LTS13632) (7).

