**Table 4 - Approximate sampled blood volume in ASMD patients ages 12 to <18 years (adolescent cohort).**

Assessment	Volume per sample (mL)	Screening period		64-week treatment period	
		Number of samples	Total (mL)	Number of samples	Total (mL)
SMPD1 genotyping	3	1	3		
UGT1A1 genotyping	3	1	3		
CHIT1 genotyping	3	1	3		
ASM activity in leukocytes	6	1	6		
Serology tests: HIV, Hep C, Hep B	7	1	7		
Liver function	3	1	3	43	129
Clinical chemistry	4	1	4	16	64
Hematology	4	2	8	16	64
Coagulation	5	1	5	16	80
β—hCG	2	1	2	0	
Safety biomarkers	8			43	344
Anti-olipudase alfa IgG and neutralizing antibodies in IgG positive patients	3.5			13	45.5
Efficacy biomarkers	5			4	20
Lipid profile	8	1	8	6	48
Serum bone-specific ALP and C-telopeptide	4			4	16
Sphingomyelin and metabolites in plasma and/or DBS	3			43	129
Olipudase alfa pharmacokinetics	2			28	56
Total for screening (mL)			52		
Total for 64-week treatment period (mL)					995.5
Total for study (mL)					1047.5

**Table 5 - Approximate sampled blood volume in ASMD patients in the child cohort (6 to <12 years) and in patients aged 3 to <6 years.**

Type	Volume per sample (mL)	Screening period		64-week treatment period	
		Number of samples	Total (mL)	Number of samples	Total (mL)
SMPD1 genotyping	3	1	3		
UGT1A1 genotyping	3	1	3		
CHIT1 genotyping	3	1	3		
ASM activity in leukocytes	3	1	3		
Serology tests: HIV, Hep C, Hep B	2.2	1	2.2		
Liver function	3	1	3	30	90
Clinical chemistry	4	1	4	11	44
Hematology	2	2	4	11	22
Coagulation	2.8	1	2.8	11	30.8
Safety biomarkers	6			30	180
Anti-olipudase alfa IgG and neutralizing antibodies in IgG positive patients	2.2			13	28.6
Efficacy biomarkers	3.8			4	15.2
Lipid profile	1.1	1	1.1	6	6.6
Serum bone-specific ALP and C-telopeptide	1			4	4
Sphingomyelin and metabolites in plasma and/or DBS	1.5			43	64.5
Olipudase alfa pharmacokinetics	1.5			24	36
Total for screening (mL)			29.1		
Total for 64-week treatment period (mL)					521.7
Total for study (mL)					550.8

See [Section 1.3](#) for additional information on sample collections based upon patient age.

**Table 6 - Approximate sampled blood volume in adolescent ASMD patients from birth to ≤2 years of age (infant/early child cohort).**

Type	Volume per sample (mL)	Screening period		64-week treatment period	
		Number of samples	Total (mL)	Number of samples	Total (mL)
SMPD1 genotyping	3	1	3		
UGT1A1 genotyping	3	1	3		
CHIT1 genotyping	3	1	3		

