#### **10.3.5 Quarterly visit procedures at Week 26 and Week 52**

The following assessments are to be completed for Week 26 and Week 52 visits:

- Tanner staging: within 24 hours prior to olipudase alfa infusion (pre-infusion).
- Complete physical exam: within 24 hours prior to olipudase alfa infusion (pre-infusion).
- Neurological exam: within 24 hours prior to olipudase alfa infusion (pre-infusion).
- Body weight, height, BMI: within 24 hours prior to olipudase alfa infusion (pre-infusion).
- Patient photos: within 24 hours prior to olipudase alfa infusion (Week 52, pre-infusion, optional).
- Doppler echocardiogram: within 24 hours prior to olipudase alfa infusion (Week 52 only, pre-infusion). Vital signs: Before (within 30 minutes prior) infusion, halfway through infusion, and after infusion ( $\pm 10$  minutes). Postinfusion vital signs are measured every 30 minutes for the first 2 hours, hourly for 2 to 6 hours postinfusion, and then once every 8 hours until the patient is discharged ( $\pm 10$  minutes).
- Vital signs: Before (within 30 minutes prior) infusion, halfway through infusion, and after infusion ( $\pm 10$  minutes). Postinfusion vital signs are measured every 30 minutes for the first 2 hours, hourly for 2 to 6 hours postinfusion, and then once every 8 hours until the patient is discharged ( $\pm 10$  minutes).
- ECG: within 24 hours prior to olipudase alfa infusion (pre-infusion), at the end of infusion (within 10 minutes following end of infusion), 24 hours and 48 hours following end of infusion ( $\pm 3$  hours).
- Clinical laboratory samples:
  - Liver function testing, clinical chemistry and coagulation: as indicated by age cohort in [Section 1.3](#) and [Section 1.4](#). Preinfusion samples to be collected within 24 hours prior to olipudase alfa infusion. Post infusion samples to be collected  $\pm 3$  hours from scheduled time.
  - Hematology

- a) Week 26: within 24 hours prior to olipudase alfa infusion (pre-infusion), 24 hours (adolescent cohort only) and 48 hours following end of infusion ( $\pm 3$  hours).
- b) Week 52:
  - Pre-infusion: Two (2) samples to be collected greater than 12 hours but less than 24 hours apart. The first sample can be collected up to 24 hours prior to olipudase alfa administration at Week 52. If necessary, the second sample may be collected following olipudase alfa infusion at Week 52.
  - 24 hours following end of infusion (adolescent cohort only,  $\pm 3$  hours).

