2.6 ANALYSIS OF SAFETY DATA

Safety endpoints include data pertaining to the safety and tolerability of olipudase alfa: assessment of adverse events (AEs)/treatment-emergent adverse events (TEAEs), including AESIs (eg, infusion-associated reactions (IARs), symptomatic overdose, etc.); physical examinations; neurological examinations; clinical laboratory evaluations; vital sign measurements; ECGs; Doppler echocardiography; liver ultrasound Doppler; safety biomarkers; and immune response assessments. For laboratory endpoints, the summaries will use both the international system of units (SI) and US conventional units; figures will use the international system of units (SI); data listings will provide the results in original units as well as in standard units, where applicable.

All the safety analyses will be performed using the safety population. Patients will be summarized and displayed by age group cohorts and overall. Safety data will be reported up to and including the time of treatment withdrawal, and follow-up for AEs, where applicable. The baseline value is the last available value before the first infusion of olipudase alfa, except for white blood cell count, platelet count, hemoglobin and possibly ECG parameters. For complete definition of baseline, refer to [Section 2.11.1](#).

For all safety data, the observation period will be divided into 2 segments:

- The **pretreatment period** is defined as the time between when the patient gives informed consent and the start of the first infusion (excluded).
- The **on-treatment period** is defined as the time from the start of the first infusion (included) till the end of the study.

The following definitions regarding potentially clinically significant abnormality (PCSA) will be applied to laboratory parameters, vital signs and ECG:

The PCSA values are defined as abnormal values considered medically important by the sponsor according to predefined criteria/thresholds based on literature review and defined by the sponsor for clinical laboratory tests, vital signs, and ECG. These values are provided in [Section 2.11.5](#).

- PCSA criteria will determine which patients had at least 1 PCSA taking into account all evaluations performed, including unscheduled or repeated evaluations.
- Before determining a value as PCSA, the value will be rounded to the precision that the PCSA criterion is defined.

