PCSA values for hematology, liver function tests and clinical chemistry (provided in [Section 2.11.5](#)) during the study (from first infusion start to last available observation) will be summarized by age group cohorts and overall. PCSA values for hematology, liver function test and clinical chemistry parameters will be provided in separate listings.

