2.11.5 Potentially clinically significant abnormalities (PCSA) criteria

In the safety data analysis, patients included in the PCSA analysis for a given parameter will be defined as subjects:

- Exposed to study treatment,
- With at least one parameter result after study treatment administration, and,
- With available laboratory limits when required for analysis.

Liver function tests

ALT	> 3 ULN By distribution analysis: > 3 ULN > 5 ULN > 10 ULN > 20 ULN
AST	> 3 ULN By distribution analysis: > 3 ULN > 5 ULN > 10 ULN > 20 ULN
Alkaline phosphatase	> 1.5 ULN
Total bilirubin	>= 1.3 ULN
ALT and total bilirubin	ALT > 3 ULN and total bilirubin > 2 ULN

Hematology

WBC	Birth/0 to 27 days old (Neonates)	<4.0 GIGA/L >25.0 GIGA/L
	28 days/1 month to 23 months old (Infants)	<4.0 GIGA/L >20.0 GIGA/L
	24 months/2 years to <6 years old (Children)	<3.0 GIGA/L >16.0 GIGA/L
	6 to <12 years old (Children)	<5.0 GIGA/L >17.0 GIGA/L
	12 to 16/18 years old (Adolescents)	<4.5 GIGA/L >13.5 GIGA/L
Lymphocytes	Birth/0 to 27 days old (Neonates)	<1.2 GIGA/L >17.0 GIGA/L
	28 days/1 month to 23 months old (Infants)	<2.0 GIGA/L >13.5 GIGA/L
	24 months/2 years to <6 years old (Children)	<1.0 GIGA/L >9.5 GIGA/L
	6 to <12 years old (Children)	<1.0 GIGA/L >8.0 GIGA/L
	12 to 16/18 years old (Adolescents)	<0.6 GIGA/L >6.0 GIGA/L

Neutrophils	Birth/0 to 27 days old (Neonates)	<4.0 GIGA/L (1 day old) <1.5 GIGA/L (2 – 7 days old) <1.25 GIGA/L (>7 day – 1 month old) >1 ULN
	28 days/1 month to 23 months old (Infants)	<1.0 GIGA/L (1 – 3 months) <1.2 GIGA/L (3 – 24 months) >1 ULN
	24 months/2 years to <6 years old (Children)	<1.2 GIGA/L >1 ULN
	6 to <12 years old (Children)	<1.2 GIGA/L >1 ULN
	12 to 16/18 years old (Adolescents)	<1.2 GIGA/L >1 ULN
Eosinophils	All age ranges	>0.5 GIGA/L Or >ULN if ULN \geq 0.5 GIGA/L
Hemoglobin	Birth/0 to 27 days old (Neonates)	<12.0 g/dL and 20% decrease from baseline, or decrease from baseline \geq 2 g/dL
	28 days/1 month to 23 months old (Infants)	<9.0 g/dL and 20% decrease from baseline, or decrease from baseline \geq 2 g/dL
	24 months/2 years to <16/18 years old (Children, Adolescents)	<10.0 g/dL and 20% decrease from baseline, or decrease from baseline \geq 2 g/dL
Hematocrit	Birth/0 to 27 days old (Neonates)	<0.39 l/l or 40% >0.61 l/l or 47%
	28 days/1 month to 23 months old (Infants)	<0.29 l/l or 29% >0.42 l/l or 42%
	24 months/2 years to <16/18 years old (Children, Adolescents)	<0.32 l/l or 32% >0.47 l/l or 47%

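### Any-time laboratory PCSA and shift percentages are not comparable across age cohorts, because only adolescents have a scheduled 24 h post-infusion sample (minor)

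*SAP*

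**What the plan says.** **Counting rule.** SAP 2.6 states that "PCSA criteria will determine which patients had at least 1 PCSA taking into account all evaluations performed, including unscheduled or repeated evaluations". The denominator in SAP 2.11.5 asks only for exposed patients "With at least one parameter result after study treatment administration", plus laboratory limits where needed. SAP 2.6.5 then tabulates PCSA "during the study (from first infusion start to last available observation) will be summarized by age group cohorts and overall". The same section gives normal-range shift tables by cohort, one of them for any time in the on-treatment period. Protocol 11.4.2.2 has the same approach: all post-baseline assessments, rechecks included, by age group.

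**Sampling schedule.** Protocol 1.3 lists liver, chemistry, coagulation and hematology draws before infusion, at 24 h and at 48 h. Its footnote c then says "Sample/assessment is not required in patients in the child cohort" and extends this to patients aged 3 to <6 years. The chart for patients aged 2 years or under (Protocol 1.4) has no 24 h column, and its footnote c also drops chemistry and coagulation at Week 12. Protocol 10.3.5 marks the hematology draw at "24 hours following end of infusion (adolescent cohort only".

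**Timing of expected changes.** Protocol 4.1 reports that in the adult single-dose study ceramide, bilirubin, hsCRP and other acute-phase reactants showed increases "that peaked 24 to 48 hours post-dose and resolved by Day 14".

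**The concern.** The proportion of patients who are ever abnormal depends on how often, and when, they are tested. Here testing differs by age cohort, which is also the column variable of the table. With the same true risk in every cohort, adding samples can leave the chance of at least one flag unchanged or raise it, but cannot lower it. The extra adolescent draw also falls in the window where the protocol expects bilirubin to move.

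Safety is the primary objective and SAP 2.6 displays all safety data by cohort. No test between cohorts is specified, so a reader will compare the percentages by eye. Part of any difference between adolescents and younger children could then come from the sampling schedule, and neither document warns of this.

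**Working it through.** **1. Reproduce the protocol's sample counts.** The inputs are the flow charts in Protocol 1.3 and 1.4, the visit procedures in 10.3, and the dose steps in 8.3.2 with no repeated or missed dose.

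- Escalation and second-highest-dose visits: Weeks 2, 4, 6, 8, 10, 14, 16, 18 = 8.
- Visits on the quarterly schedule: Weeks 0, 12, 26, 38, 52 = 5. Week 0 and Week 12 follow the quarterly schedule without duplication (Protocol 10.3).
- Other visits before Week 26, pre-infusion liver test only: Weeks 20, 22, 24 = 3.
- Week 64: one liver and one chemistry sample, no hematology.

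| | Adolescent | 3 to <12 y | 2 y or under |
|---|---|---|---|
| Liver | 13×3+3+1 = 43 | 13×2+3+1 = 30 | 8×2+4×2+1+3+1 = 29 |
| Chemistry | 5×3+1 = 16 | 5×2+1 = 11 | 1+3×2+1 = 8 |
| Hematology | 5×3+1 = 16 | 5×2+1 = 11 | 1+4×2+1 = 10 |

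The added 1 in the first two hematology cells, and the last 1 in the third, is the second Week 52 sample. All nine counts match Protocol Tables 4 to 6. The adolescent liver row, for example, reads "Liver function 3 1 3 43 129", that is, 43 treatment-period samples.

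**2. Samples that can produce a PCSA.** The Day 1 pre-infusion draw is not post-baseline, so it is removed. Patients aged 2 or under have no such draw for these tests.

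- Liver: 42 / 29 / 29 (42/29 = 1.45).
- Chemistry: 15 / 10 / 8 (15/10 = 1.50; 15/8 = 1.88).
- Hematology: 15 / 10 / 10 (1.50).

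The infant/early child cohort (birth to <6 years) mixes the second and third schedules.

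**3. Effect at equal risk.** The documents give no per-sample PCSA probability p, so p is an assumption. With independent samples, P(at least one PCSA) = 1 − (1 − p)^n.

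| p | Liver, 42 vs 29 | Ratio | Chemistry or hematology, 15 vs 10 | Ratio |
|---|---|---|---|---|
| 1% | 34.4% vs 25.3% | 1.36 | 14.0% vs 9.6% | 1.46 |
| 2% | 57.2% vs 44.3% | 1.29 | 26.1% vs 18.3% | 1.43 |
| 5% | 88.4% vs 77.4% | 1.14 | 53.7% vs 40.1% | 1.34 |

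**4. Sensitivity to correlation (liver, p = 2%).** These correlations are assumed and apply to the underlying continuous values.

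- Correlation 0.8 between the 24 h and 48 h values of one visit, other draws independent: 52% vs 44%, ratio 1.18.
- The same, plus a correlation of 0.4 to 0.6 across all of a patient's samples: ratio about 1.15.

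**5. Sensitivity to how long excursions last.** Suppose a 2% chance of an excursion at each of 13 infusions, and count only the 24 h and 48 h draws.

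- All persist to 48 h: 23.1% vs 23.1%, ratio 1.0.
- 20% visible only at 24 h: 23.1% vs 18.9%, ratio 1.22.
- 50% visible only at 24 h: 23.1% vs 12.2%, ratio 1.89.

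This version leaves out the shared pre-infusion draws, which dilute the ratio in the real table.

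**6. Check of the remedy.** Dropping the 24 h draws gives liver 42 − 13 = 29 / 29 / 29, hematology 15 − 5 = 10 / 10 / 10 and chemistry 15 − 5 = 10 / 10 / 8. Dropping the two Week 12 chemistry draws as well gives 8 / 8 / 8.

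**The case against.** The case for leaving the tables alone has several sound parts.

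- **Like-for-like summaries exist.** SAP 2.6.5 also plans observed values, changes and normal-range shifts at scheduled time points by cohort, by-patient plots of key parameters, and PCSA listings. A reader can compare 48 h with 48 h. This stands, but none of these is a PCSA summary at common time points.
- **Descriptive tables, few patients.** The adolescent minimum is 3. At 57% and 44%, 3 patients give 1.7 and 1.3 expected flags, a difference of 0.4 of a patient. This stands and lowers the severity. It does not remove the built-in difference in ascertainment.
- **The 48 h draw is also in the peak window**, and every cohort has it. Ceramide, hsCRP, iron and ferritin have no PCSA criterion, and Protocol 6.4.1.1 says the increases were attenuated under dose escalation. This stands: the timing argument is weaker than it first looks.
- **Thresholds vary by age.** The lower WBC limit is 5.0 GIGA/L at 6 to <12 years and 4.5 in adolescents. The creatinine limit is 90 against 132 µmol/L. These could offset or add to the sampling effect.
- **The draw is only not required.** Any unscheduled 24 h samples in younger patients would count and narrow the gap.

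Two stronger readings are tempting. A reader might set 26 post-infusion liver draws against 13 and infer, at p = 2%, a gap of 41% against 23%. That omits the 16 other draws after the first infusion that both groups share and that the PCSA rule counts. A reader might also infer that adolescents will look worse on every laboratory table. The age-specific limits do not support that outside the liver tests.

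**Conclusion.** The point holds as a minor one. The unequal sampling is a fact of the schedule and reproduces exactly. The any-time PCSA and any-time shift tables pass it straight into the cohort columns. At equal underlying risk it tends to raise the adolescent percentage. The direction is clearest for liver tests, where the criteria are the same multiples of ULN at all ages. For hematology and creatinine, age-specific thresholds leave the net direction unknown.

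The size cannot be derived from the documents. At an assumed 2% per sample with independence it is 57% against 44% for liver tests (ratio 1.29), and 26% against 18% for 15 against 10 chemistry or hematology samples. Correlation within patients brings the liver ratio to about 1.15 to 1.18, and it is 1.0 if every excursion seen at 24 h persists to 48 h. It would be larger if many excursions were visible only at 24 h, which the documents neither show nor exclude. The issue is how a descriptive table is read. No error rate is affected, and the overall column and the individual listings remain valid.

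**What to change.** In SAP 2.6.5:

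1. Keep the any-time PCSA and shift tables on all evaluations, so that no safety signal is lost.
2. Add a by-cohort version of both, limited to post-baseline time points scheduled in every cohort. Exclude the 24 h draws. For chemistry, also exclude Week 12 and the Day 1 pre-infusion draw, which is not post-baseline.
3. Show the number of evaluations per patient beside each cohort percentage.
4. Add a footnote that 24 h laboratory samples were scheduled in adolescents only.

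The cost is one filtered rerun of existing tables on data already collected. No procedure or sample changes.

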2.6.6 Vital signs

Vital signs are to be measured at every visit before, halfway through, and after infusion (± 10 minutes). Post-infusion vital signs are measured every 30 minutes for the first 2 hours, hourly for 2 to 6 hours post-infusion, and then once every 8 hours until the patient is discharged (± 10 minutes). Refer to [Section 2.11.1](#) for the baseline definition.

Vital signs will include heart rate (HR, beats/minute), systolic and diastolic blood pressure (SBP/DBP, mmHg), and body temperature ($^{\circ}\text{F}$ or $^{\circ}\text{C}$). Each vital sign parameter will be summarized as observed parameter value and change from baseline per-infusion, 3 hours post-infusion, 24 hours post-infusion, 48 hours post-infusion, 72 hours post-infusion and end of infusion at each scheduled visit by age group cohorts and overall.

PCSA values during the study (from first infusion start to last available observation) will be summarized by age group cohorts and overall.

